11. STUDY MONITORING

The investigator will be visited on a regular basis by the Clinical Study Monitor, who will check completed source documentation, discuss the progress of the study and monitor drug according to good clinical practice (GCP). The monitoring will also include source data verification (SDV).

Source Data Verifications

Monitor and/or regulatory authorities will be allowed audits at the investigation site for the purpose of source data verification, in which a case review of those parts of the hospital records relevant to the study must be required. Data recorded in the CRF must be current at the time of the scheduled monitoring visit.

The Principal Investigator ([name]. M.D. Anderson Cancer Center) will be responsible for writing the protocol, ensuring any modifications to the study protocol must be reviewed and approved by the NCI prior to implementation, and for publishing study results.

The Protocol Lead Investigator is responsible for reviewing all case report forms and documenting his/her review on evaluation forms, discussing the contents of the reports with the Statistician, and for publishing study results. He/She will, together with the study group, be responsible for data cleaning. He/She will also generally be responsible for answering all clinical questions concerning eligibility, treatment, and the evaluation of the patients. He/She is responsible for arranging for the retention of the patient identification and the code list for at least 15 years after completion of the study. Patient files and other source data shall be kept for a maximum period of time permitted by each hospital. All information concerning the study should be stored in safe places inaccessible to unauthorized personnel. Unique study IDs will be assigned to identify the study participants. The cross-reference of study ID and patient ID will be stored in a secure file at each site and will be accessible only to

authorized personnel. All the subsequent study coordination including information sent to M. D. Anderson Cancer Center will be based on study ID to protect the patient confidentiality.

Treatment termination for any reason except completion of the study will be fully documented in the source documentation. Patients leaving the study before end-point should, if possible, go through the same final evaluations as patients completing the study according to the protocol. Every reasonable effort should be made to maintain patient's protocol compliance and participation in the study. The investigator will monitor patient protocol compliance at each follow-up visit.

Should a patient discontinue the study for any reason, the patients should be urged to return for a final visit (with an early termination evaluation preferably performed within 14 days after discontinuation from the study).

The IND sponsor and the National Cancer Institute will approve changes to the protocol or discontinuation of the study. Amendments or discontinuation of the study will be forwarded to each site for review and approval by their respective IRBs.

12. STATISTICAL CONSIDERATIONS

12.1 Study Design

The basic trial design is described earlier. The proposed study will be a double-blinded, placebo-controlled randomized study to evaluate the chemopreventive effect of erlotinib in a high-risk group of oral IEN patients. We plan to recruit a total of 150 patients in 2 years with an additional 2.5 years of follow-up. The total study period will be 4.5 years. Interim analyses will be conducted at the ends of year 2.5 and year 3.5, and the final analysis will be done at the end of year 4.5. We expect a small percentage of early drop out or loss to follow-up (10%) due to the nature of higher compliance of the elevated risk groups, tolerable toxicity profile of the agent, and intense follow up in this population.

12.2 Analysis of Primary Endpoint

The primary endpoint of the study is cancer-free survival defined as time from randomization to the development of histologically confirmed oral cancer. All patients will be analyzed on an intent-to-treat basis (i.e., as randomized). Patients lost to follow-up due to refusal or death from other causes will be censored at their time of last follow-up. The distribution of time to oral cancer development will be estimated by the Kaplan-Meier method. For randomization purposes, eligible patients will be stratified (1) by prior oral cancer status (no prior oral cancer versus prior oral cancer) and (2) broadly by registration site (M. D. Anderson versus non-M. D. Anderson site). Within each stratum, Pocock-Simon dynamic allocation method will be applied to achieve balanced randomization with respect to potentially important factors including current, former and never smoking. Patients will be randomized into the erlotinib arm or the placebo arm with equal probability. Stratified log-rank test will be used to compare cancer-free survival among treatment groups. The Cox (proportional hazards) regression model will be used to incorporate potential prognostic factors and treatment assignment as covariates. Details of the assumptions used for the sample size calculation are listed below.

1. The study has a 2-year period to accrue 100 oral IEN/prior cancer and 50

IEN-alone patients, with an additional 2.5-years follow-up. The total study duration is 4.5 years.

2. The anticipated yield of LOH screening (described earlier) will be approximately 66% in the IEN/LOH-cancer history group and 28% in the IEN/LOH-alone group. Assuming accrual rates of 60% (eligible, cancer history) and 45% (eligible, no cancer history), we will need to screen a total of 253 oral IEN patients with and 365 (accounting for year-2 accruals who were screened, eligible, and did not volunteer in year 1) oral IEN patients without a history of curatively treated oral cancer at all four participating centers in order to reach our total accrual goal.
3. Time-to-oral cancer development follows an exponential distribution. Based on the data described earlier, 65% of the patients with IEN/LOH associated with curatively treated oral cancer will develop oral cancer in three years, and 35% of the IEN/LOH-alone patients will develop oral cancer in three years.
4. Erlotinib, the active treatment, can reduce the 3-yr oral cancer rate by 40% for the IEN/LOH-cancer history group, i.e., 3-year cancer rate will be reduced from 65% to 39%. This corresponds to a hazard ratio of 0.47. We assume the same treatment effect (hazard ratio) in the IEN/LOH-alone group, corresponding to the 3-yr oral cancer rate reduction from 35% to 18%. The parameters, lambda, for the exponential distributions are 0.3499 (control) and 0.1648 (treatment) in IEN/LOH-cancer history patients and 0.1436 (control) and 0.0676 (treatment) in IEN/LOH-alone patients, respectively.
5. We assume the rate of lost-to-follow up, which includes patient refusal, early drop out, or competing risk, etc. is 10%. The distribution of the time to loss to follow-up is assumed to be uniform.
6. Stratified log-rank test (**stratify by the randomization stratification factors**) is used to compare the cancer-free survival between the active and control groups.
7. Two interim analyses are planned – one at the end of year 2.5 and another one at the end of year 3.5. The final analysis will be performed at the end of year 4.5. We will apply the group sequential design with the O'Brien-Fleming boundary to control the overall two-sided type I error rate to 5%. The levels of significance for the first, second, and third tests are 0.0005, 0.014, 0.045, respectively.

Based on the above assumptions, we ran simulation studies with 10,000 replications. The results show that a total of 150 patients will allow us to have 85% power with a two-sided 5% type I error rate.

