1.2.3.12 Genome wide single nucleotide polymorphisms, telomere length, mitochondrial DNA alterations

2. BACKGROUND

2.1 Study Disease—Oral Carcinogenesis

Oral squamous cell carcinoma (OSCC) is a disfiguring, aggressive epithelial malignancy associated with high mortality and severe morbidity in long-term survivors. More than 300,000 annual new cases are diagnosed worldwide. Treating oral leukoplakia, the most common oral IEN and a precursor lesion of oral cancer, varies from watchful waiting to complete resection.^{1,2} The prevalence rate of oral IEN ranges from 2%-8% in older persons.³ Oral cancer incidence is increasing, and oropharyngeal cancer is the sixth most common cancer in adults in western countries. Almost 50% of the patients in the oncology departments of some developing countries suffer from oral cancer. Despite recent advances in screening and treatment, the long-term survival of patients with OSCC has only marginally improved over the past three decades, only 50% of OSCC patients survive 5 years after diagnosis.¹⁻⁴

Etiology

Epidemiologic data established tobacco and alcohol use as the major causes of oral cancer.⁴⁻⁷ Oral cancer risk is almost 10 times greater in individuals who do than who do not smoke and drink and almost 100 times greater in persons who smoke and drink heavily. A substantial percentage of the people with these risk behaviors, however, do not develop cancer. Other OSCC risk factors are betel quid chewing and possibly marijuana use.⁸ These factors, and tobacco and alcohol use, also increase the risk of oral IEN.⁹ The risk of oral cancer with any type of unfiltered cigarette is twice that of filtered cigarettes,⁶ and the risk associated with hand-rolled unfiltered cigarettes is higher than that of factory-made unfiltered cigarettes.¹⁰

Although human papilloma virus (HPV) infection has been hypothesized for decades to play a role in the etiology of oral neoplasia, various studies have found different and contradictory frequencies of HPV DNA detection in oral mucosal lesions.^{11,12} Recent data from the largest sample size yet analyzed could not establish a link between HPV infection and the development of either regular or more-aggressive verrucous oral IEN.¹³ Nevertheless, HPV may be involved in some patients who develop oral neoplasia, for example, in a subset of OSCC patients without tobacco or alcohol risk factors.

Multifocal, Multistep Carcinogenesis

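### Smoking steers the allocation but is not in the primary log-rank test; if smoking is prognostic, that test is conservative and gives up some power

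*Combined protocol and SAP*

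**What the plan says.** Section 12.2 (Analysis of Primary Endpoint) names two stratification factors, prior oral cancer and site (M. D. Anderson or elsewhere). Inside each stratum, "Pocock-Simon dynamic allocation method will be applied to achieve balanced randomization with respect to potentially important factors including current, former and never smoking". The word 'including' leaves the list of balancing factors open.

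Item 6 of the sample-size assumptions in the same section sets the primary log-rank test to "stratify by the randomization stratification factors". Smoking is introduced as a dynamic-allocation factor and not as a stratification factor, so the plain reading is a four-stratum test without it. The text never says so outright. Section 6.5 also speaks of stratified randomization with dynamic allocation and does not separate the two kinds of factor.

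Section 12.2 also plans a Cox model with treatment and prognostic covariates. It does not name the covariates, and it is not the primary test.

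The sample-size assumptions contain no smoking effect. The only relevant figure is background, in Section 2.1: "Oral cancer risk is almost 10 times greater in individuals who do than who do not smoke and drink".

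On power and error: "The results show that a total of 150 patients will allow us to have 85% power with a two-sided 5% type I error rate", and "The levels of significance for the first, second, and third tests are 0.0005, 0.014, 0.045, respectively".

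**The concern.** The variance of the log-rank statistic allows for chance differences between arms in any prognostic factor that is not in the strata. Dynamic allocation removes most of that chance difference for smoking. If smoking affects the hazard, the statistic then varies less than its variance formula assumes, and the true rejection rate under the null falls below the nominal level. Separately, leaving out a prognostic covariate pulls the estimated hazard ratio towards 1 relative to the effect within smoking groups. Both cost power, in a trial that expects about 69 events.

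There is also a question of pre-specification. Item 6 could be run with four strata or, by a reader who counts smoking as a randomization factor, with twelve. The Cox covariates could be chosen after the data are seen.

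**Working it through.** **Inputs from Section 12.2.** 100 patients with prior cancer and 50 without; 2-year accrual and 2.5 further years; looks at years 2.5, 3.5 and 4.5 at 0.0005, 0.014 and 0.045; exponential hazards 0.3499 and 0.1648 (prior cancer) and 0.1436 and 0.0676 (no prior cancer); 10% loss, uniform in time; 1:1 allocation.

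**Assumptions, because the documents are silent.** 60% of patients at M. D. Anderson; biased coin of 0.8 for the dynamic allocation on smoking; smoking mix 25/45/30% current/former/never; current-versus-never hazard ratio from 1 to 4, with former at its square root.

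**Step 1: hazard ratio.** −ln(0.35)/3 = 0.3499 and −ln(0.61)/3 = 0.1648, ratio 0.47. This agrees with the plan.

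**Step 2: the plan's power.** Simulating the plan with no smoking effect (10,000 replicates) gives 0.856 in the base case and 0.848 to 0.869 across allocation and dropout variants, with about 69 events at the final look. Cross-check by Schoenfeld's formula at 68.7 events and alpha 0.045: Φ(√68.7/2 × |ln 0.47| − 2.005) = Φ(4.144 × 0.755 − 2.005) = Φ(1.12), about 0.87. The stated 85% reproduces.

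**Step 3: overall type I error over three looks** (20,000 replicates; simulation standard error about 0.0015).

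| Smoking HR | Planned log-rank | Planned, deterministic allocation | Cox with smoking covariate |
|---|---|---|---|
| 1 | 0.0485 | 0.0494 | 0.0488 |
| 1.5 | 0.0467 | 0.0442 | 0.0474 |
| 2 | 0.0440 | 0.0452 | 0.0478 |
| 3 | 0.0390 | 0.0381 | 0.0482 |
| 4 | 0.0341 | 0.0338 | 0.0464 |

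The mechanism can be checked by hand. In the biased-coin runs the planned statistic had a standard deviation of 0.964 at HR 3 and 0.937 at HR 4. A single final test at 1.96 should then reject with probability 2{1 − Φ(1.96/0.964)} = 0.042 and 2{1 − Φ(1.96/0.937)} = 0.036. The simulated single-look rates were 0.0420 and 0.0364.

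**Step 4: power over three looks, hazard ratio 0.47 within smoking groups** (10,000 replicates; standard error about 0.0035 per entry; all tests applied to the same simulated trials).

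| Smoking HR | Planned (4 strata) | Cox with smoking covariate | Log-rank, 12 strata | Cox minus planned |
|---|---|---|---|---|
| 1 | 0.864 | 0.860 | 0.850 | −0.4 points |
| 1.5 | 0.853 | 0.853 | 0.838 | 0.0 |
| 2 | 0.854 | 0.861 | 0.849 | +0.7 |
| 3 | 0.843 | 0.863 | 0.849 | +2.0 |
| 4 | 0.817 | 0.863 | 0.846 | +4.6 |

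**Step 5: the protocol's cohort-level 3-year rates held fixed** (65% to 39% and 35% to 18%). Planned against Cox: 0.864 and 0.873 at HR 2, 0.870 and 0.893 at HR 3, 0.866 and 0.899 at HR 4. The gains are 0.9, 2.3 and 3.3 points, and the planned test stays above 85%.

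**Step 6: smoking as further strata.** In the step 4 table, twelve strata lose about 0.5 to 1.5 points against the planned test at HR 1 to 2 and gain only from HR 3. A covariate with 2 degrees of freedom inside the four strata avoids that loss.

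**Step 7: second check.** A smaller simulation of the final look alone (3,000 replicates per cell) gave planned power of 85.0, 84.2, 80.5 and 77.9% at HR 1, 2, 3 and 4, against 84.6, 84.9, 83.9 and 83.6% with the covariate. It agrees on direction. The three-look figures are the ones to use for size, since the plan has three looks and they rest on more replicates.

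**The case against.** The strongest reply is that the loss depends on a number the documents do not contain. The Section 2.1 figure compares people who smoke and drink with people who do neither, and it concerns the occurrence of oral cancer in general. It does not describe progression among patients already selected for LOH-positive lesions, and Section 12.2 itself treats smoking only as possibly important. At HR 1 to 1.5 nothing is gained by adjusting, and at HR 2 the gain is 0.7 points. This stands, and the point has to be stated conditionally.

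Two further replies also stand. The four-stratum log-rank test is valid without a model for smoking. And the fall to 0.817 at HR 4 arises from holding 0.47 within smoking groups, whereas the protocol states cohort rates averaged over smoking; on that scale power stays at 0.864 to 0.870 for HR 2 to 4.

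It can also be said that item 6 is ambiguous and that an adjusted Cox model is already planned. Both are true but do not settle the matter. Counting smoking among the strata gives the twelve-stratum test, which does worse at modest smoking effects. The Cox model is not primary and names no covariate.

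A reader might go further and infer that the trial is underpowered, that the 85% is wrong, or that type I error is out of control. The documents support none of these. The 85% reproduces, and the error rate moves only downwards as the smoking effect grows.

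**Conclusion.** On the plain reading of Section 12.2, smoking balances the allocation and is absent from the primary test. If smoking is prognostic here, the test is conservative: overall type I error about 0.044, 0.039 and 0.034 at assumed hazard ratios of 2, 3 and 4, against about 0.048 with no smoking effect. The power forgone against a smoking-adjusted Cox test is about 0.7, 2.0 and 4.6 points with the treatment effect fixed within smoking groups, or 0.9, 2.3 and 3.3 points with the protocol's cohort rates fixed. Up to a hazard ratio of about 2 the cost is negligible. The sizes rest on the assumed smoking effect, smoking mix, site split and biased coin.

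This is unused efficiency plus an unclear specification. It is not a fault of validity or a shortfall in the stated power. The case for acting is the asymmetry: adjusting costs about 0.4 points if smoking is irrelevant and recovers several if it is strongly prognostic. Label: cheap improvement.

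**What to change.** In Section 12.2:

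1. Make the primary test the treatment term of a Cox model stratified by prior oral cancer and site, with smoking (current, former, never, as recorded for the allocation) as a covariate. Name the form of the test (Wald, score or likelihood ratio).
2. List every factor used in the dynamic allocation and enter each one as a covariate in the same way.
3. Keep the three looks and their significance levels.
4. Report the log-rank test stratified by prior cancer and site as supportive, and state in item 6 that its strata are those four.
5. Do not add smoking as further log-rank strata.

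The cost is a few sentences. Smoking status is already collected before randomization (Sections 7.1 and 7.2) and is needed for the allocation. The downsides are a mild modelling assumption for the smoking effect, a treatment hazard ratio that is conditional on smoking, and about 0.4 points of power if smoking turns out not to be prognostic.

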13. ETHICAL AND REGULATORY CONSIDERATIONS

13.1 Ethical Standards and Notifications

This trial will be conducted in compliance with the protocol, Good Clinical Practice (GCP), and the applicable regulatory requirements.

13.2 IRB Approval

The study will be reviewed by the IRBs at M. D. Anderson Cancer Center, Memorial Sloan Kettering Cancer Center, Emory University, University of Chicago, and the University of Maryland. The protocol will also be reviewed by the National Cancer Institute and the FDA.

13.3 Patient Data Protection and Confidentiality

Each study participant will be assigned a unique study ID number to assure confidentiality.

Each investigator is responsible for keeping a master list of all enrolled patients including their name, unique study ID number, phone number(s) and last known address.

The patients will also be informed in the informed consent document about the possibility of audits by authorized representatives of the NCI, FDA, OSI Pharmaceuticals or study monitors, in which case a review of those parts of the hospital records relevant to the study may be required, with due consideration of the patient confidentiality. New pathology accession numbers will be assigned for specimen identification versus patient hospital numbers. Once assigned, these numbers are cross-referenced in a secure database maintained by the study statistician at M. D. Anderson Cancer Center.

In the event of a breach of confidentiality, all investigators and the sponsors will be notified. Appropriate action will be taken following consultation with these representatives, as well as with the involved patient(s). Actions could include but will not necessarily be limited to withdrawal of the patient(s) from the study or recording of the patient(s) data.

13.4 Informed Consent

The investigator is responsible for giving and documenting the patients full and adequate verbal and written information about the nature, purpose, possible risks and benefits of the study. This will include information that (a) this is a placebo controlled trial, (b) the study agent must be taken daily for the 1 year duration of the intervention, (c) they must be willing to have biopsies and give blood at the specified times, (d) specified follow-up visits with physicians and study clinics must be scheduled and kept, and (e) side effects and health risks may occur, as described in the consent form.

The patients will be given the opportunity to refuse to participate in the study, under the assurance that such refusal will in no way affect their treatment at their study center. The patients must also be notified that they are free to withdraw from the study at any time. The investigator and study research nurse are responsible for obtaining signed informed consent from all participants. This consent form fulfills the requirements set by the Institutional Review Board at M. D. Anderson Cancer Center, Memorial Sloan Kettering Cancer Center, Emory University, the University of Chicago, and the University of Maryland. It fully describes the procedures, risks, alternatives and potential benefits as required by FDA specifications. A copy of the signed consent form will be placed in the patient's medical record, and a separate copy will be maintained in the research file. Another copy will be given to the patient for his or her own record.

14. FINANCIAL SUPPORT AND DISCLOSURE

14.1 Financial Support

The study is funded by grant P01-CA-106451 from the US National Cancer Institute (NCI). OSI Pharmaceuticals will support the study by providing active drug and matched placebo and provide funds specifically for monitoring this multicenter study. The NCI and OSI Pharmaceuticals will, if requested, have the right to review and comment upon any manuscripts prior to submission for publication.

